## Place of study

The base-line study was conducted within 2.5 months, the intervention was applied within 3 months and the follow up study with final evaluation was within 12 months, in 2019–22 in Metropolitan Cucuta in the North-East of Colombia, including the city of Cucuta (629,414), and two adjacent municipalities Villa del Rosario (93,735) and Los Patios (81,411 inhabitants) located in the Norte de Santander state [1]. The climate is warm and dry, with a mean annual temperature of 26.7 °C and annual rainfall of 806 mm. There are two rainy seasons from the end of March to the beginning of June and from the end of September to the beginning of December. DZC are endemic, with occasional epidemic outbreaks [2].

## Study design and sample size to baseline study and evaluation

This is design study for a large cluster randomized trial on the impact of treating water containers with a protective paint. The sample size was calculated for detection of a 50% reduction in the House Index with > 99% power at 5% significance level. Given a baseline HI of 30%, an intra-cluster correlation coefficient (ICC) of 0.01 and a cluster size of 2,000 households it was found that a minimum of 12 clusters per study arm was needed [3]. The same result but with a lower power (68%) was found for a baseline DZC incidence of 3% and a 50% reduction in the intervention arm. A large number of households per cluster was needed as *Ae. aegypti* vectors are day-biters [4,5,6] and it was assumed that many household members stay within their neighbourhoods during the day (mainly housewives, small children and school children when the school is close to their house) where they are at risk to get infected. All estimations were done through The Shiny CRT Calculator which is a web-based app to determine sample size and power for cluster trials [7].

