## Sampling procedure for household survey and entomological inspections

On the basis of available maps, the city was stratified into high, middle and low endemic/infested areas for *Ae. aegypti* (strata) using the surveillance information from SIVIGILA of the preceding year as well as information obtained from interviews with the vector control coordinators in Cúcuta. By this way, 24 high and medium endemic areas (clusters) were selected in Cucuta (16 clusters), Los patios (4 clusters) and Villa del Rosario (4 clusters). Figure 1 shows the selected clusters in

Cucuta to be sampled by staff. For the baseline study they were not yet paired and allocated to the intervention and control arm as this was planned to do with the information resulting from the baseline study enabling us to find pairs of clusters with similar characteristics. The following characteristic should be similar in each pair of clusters: (I) High and middle level endemicity for *Aedes*-borne diseases; (II) Similar socio-economic conditions; (III) Similar types of the built environment: houses, schools, industry, health centers, workshops, churches and stores; (IV) Similar characteristics of public spaces. Within each cluster, all blocks of houses were inspected including public spaces. For the entomological/socio-demographic household survey, a proportion of 10% of 2000 houses was sampled in this study, resulting in 200 houses in each cluster. This number was rounded to 250 by convenience. Therefore, the study targeted 6000 households (250 households in each cluster) using a systematic random sampling method. For this we first estimated the sampling interval by dividing the total number of households in each cluster (around 2000) by the number of sample households (250), resulting in a sampling interval of 8. All households located within each cluster were mapped and a randomly defined starting point was selected and from there every 8th household was visited. Clear replacement rules were given to the interviewers and the compliance was checked in sample of families.

Vector control staff and trained interviewers participated in the survey. They were divided into “couples” of one vector inspector and one interviewer. Each couple was assigned one cluster where they had to visit the sample houses. The interviewer did the interview with the head of household and simultaneously the inspector (local vector control staff) did the inspection of water containers both of them filling a form.

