## Household questionnaire

Demographic and health data was collected through face-to-face interviews using a standard questionnaire that included both structured and semi-structured questions. Household questionnaire was adapted from published research in Colombia [8]. The questions referred to socio-demographic parameters (number of people living in the house, age, sex, and educational level), self-reported DZC disease acquired during the last months, population mobility during the day, usage of water in tanks and willingness to accept the intervention trial (see Additional file).

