## Dengue surveillance and case definition

Data of the national surveillance system were obtained from SIVIGILA (the national health surveillance system), aggregated by year and setting (study areas) over the study period. Notified dengue cases including those classified as dengue fever (DF) and severe dengue, relying on a clinical case definition or lab confirmed or hospitalized patients. This study used annual population data (from the National Institute of Statistics-DANE; [10]) for calculating the incidence rate.

[figure not shown]

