#### Part A: Household sociodemographic characteristics

Person	Age	Sex 1=F 2=M 3=O	Education Primary school=1 High school= 2 University= 3 No= 4	During this year, did you or anyone in your household have DZC? 1=Dengue 2=Zika 3=Chikunguna 4=No	Which month?	Did you go to the doctor or health unit? 1=Yes 2=No	During the day, where do you spend most of the time (7 am -5 pm)? 1=Inside neighborhood, 2=Outside neighborhood
1							
2							
3							
4							
5							
6							
7							
8							
9							
10							
11							
12							

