Control of Aedes breeding sites with a dual-action insecticidal coating is effective in reducing Dengue transmission: Cluster-randomised Controlled Trial Study

Statistical Analysis Plan

Ubication of study: Metropolitan Area of Cucuta, Colombia

Approval of the protocol: 11 March 2019

Statistical Analysis Plan

Study design and sample size

This is design study for a large cluster randomized trial on the impact of treating water containers with a protective paint. The sample size was calculated for detection of a 50% reduction in the House Index with > 99% power at 5% significance level. Given a baseline HI of 30%, an intra-cluster correlation coefficient (ICC) of 0.01 and a cluster size of 2,000 households it was found that a minimum of 12 clusters per study arm was needed [1]. The same result but with a lower power (68%) was found for a baseline DZC incidence of 3% and a 50% reduction in the intervention arm. A large number of households per cluster was needed as *Ae. aegypti* vectors are day-biters [2] and it was assumed that many household members stay within their neighbourhoods during the day (mainly housewives, small children and school children when the school is close to their house) where they are at risk to get infected. All estimations were done through The Shiny CRT Calculator which is a web-based app to determine sample size and power for cluster trials [3,4].

Data management and analysis

Descriptive analyse and double data entry was practiced (to minimize data entry errors) into a database using Microsoft Office Excel software by an assistant and supervised by the research team. The analysis was done using SPSS software version 28.0.1.1.

Socio-demographic data were entered in a database. We assessed the frequency of variables potentially associated with the outcomes of recent dengue virus infection (sex, age, educational level, peoples` mobility) and selfreported dengue fever in household members (5). Persons' Chi-square test (χ^2) was applied to determine the differences between population characteristics and DZC selfreported cases, and peoples` mobility across all settings. All statistical analyses were performed at a 0.05 significance level.

Entomological indices were analysed per cluster and overall to show the presence, distribution and abundance of *Ae. aegypti* and the breeding sites most productive for adult mosquitoes were identified [6].

House index (HI): Percentage of houses infested with larvae and/or pupae.

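### Twelve clusters per arm is not the minimum for the stated House Index power, and the 68% disease power describes whole clusters, whereas DZC is recorded only in a survey of 250 households per cluster

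*Protocol*

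**What the plan says.** The protocol section on study design and sample size aims at a 50% reduction in the House Index from 30%, with more than 99% power at the 5% level and an ICC of 0.01. It concludes that with "a cluster size of 2,000 households it was found that a minimum of 12 clusters per study arm was needed [3". The SAP section Study design and sample size says the same: "a cluster size of 2,000 households it was found that a minimum of 12 clusters per study arm was needed [1".

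The disease statement follows at once: "The same result but with a lower power (68%) was found for a baseline DZC incidence of 3" per cent, again halved by the intervention. It gives no ICC, cluster size, unit or data source of its own.

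Three other places bear on this:

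- **Survey size.** Protocol, sampling procedure: "the study targeted 6000 households (250 households in each cluster) using a systematic random sampling method".
- **DZC.** Protocol, Household questionnaire: the survey collects "self-reported DZC disease acquired during the last months". The form asks, in a table with one row per person, "During this year, did you or anyone in your household have DZC".
- **Surveillance.** Protocol, Dengue surveillance and case definition: the SIVIGILA data are "Notified dengue cases including those classified as dengue fever (DF) and severe dengue", "aggregated by year and setting (study areas) over the study period". The SAP's section on data management and analysis compares annual SIVIGILA dengue incidence between intervention and control clusters.

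**The concern.** An ICC of 0.01 and a fall from 30% to 15% make an easy target for clusters of 2,000 households. Twelve per arm looked far too many to be the smallest number that reaches 99%. If so, both documents misreport why 24 clusters were needed.

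The second issue is what the 68% describes. The SAP title claims an effect on dengue transmission, so readers will use the disease power to weigh a null or borderline result. The sentence names DZC, which comes from 250 households per cluster, yet it sits beside a cluster size of 2,000. The outcome counted over whole clusters is a different one, notified dengue.

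**Working it through.** **Inputs from the documents.** House Index p1 = 0.30, p2 = 0.15; disease p1 = 0.03, p2 = 0.015; ICC 0.01; m = 2,000 per cluster (sample-size section) or 250 (survey); k = 12 clusters per arm; 5% level. Assumed: a two-sided test (sidedness is not stated), and an unpaired, post-intervention comparison.

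**Formulas.** Design effect DE = 1 + (m − 1) × ICC. SE = √{[p1(1 − p1) + p2(1 − p2)] × DE / (k × m)}. Normal power = Φ(|p1 − p2|/SE − 1.96). The t version uses the noncentral t with 2k − 2 degrees of freedom and noncentrality |p1 − p2|/SE.

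**Step 1: the plan's own powers at 12 per arm, m = 2,000.** DE = 1 + 1,999 × 0.01 = 20.99.

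- House Index: variance sum 0.21 + 0.1275 = 0.3375. SE = √(0.3375 × 20.99 / 24,000) = 0.01718. Effect/SE = 0.15/0.01718 = 8.73. Power is about 100%, so the claim of more than 99% is true.
- Disease: variance sum 0.0291 + 0.014775 = 0.043875. SE = √(0.043875 × 20.99 / 24,000) = 0.00619. Effect/SE = 2.4215. Power is 67.8% (normal) or 63.9% (noncentral t). The stated 68% reproduces.

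**Step 2: smallest k for more than 99% House Index power.** With m = 250, DE = 1 + 249 × 0.01 = 3.49.

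| m | k | Effect/SE | Normal | Noncentral t |
|---|---|---|---|---|
| 2,000 | 2 | 3.56 | 94.6% | – |
| 2,000 | 3 | 4.37 | 99.2% | 89.6% |
| 2,000 | 4 | 5.04 | 99.9% | 98.5% |
| 2,000 | 5 | 5.64 | >99.9% | 99.8% |
| 250 | 3 | 3.79 | 96.6% | – |
| 250 | 4 | 4.37 | 99.2% | 95.0% |
| 250 | 5 | 4.89 | 99.8% | 98.9% |
| 250 | 6 | 5.35 | >99.9% | 99.8% |

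The minimum is 3 (normal) or 5 (t) at 2,000 households, and 4 or 6 at 250. Beta-binomial simulation with an unpaired t-test on cluster proportions (100,000 runs per setting) agrees with the t figures: 98.5% and 99.8% for k = 4 and 5 at m = 2,000; 98.8% and 99.7% for k = 5 and 6 at m = 250.

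**Step 3: could another method give 12?** One- or two-sided tests, paired degrees of freedom, and a variance doubled for an unadjusted difference-in-differences were also tried. With doubled variance the minimum is 5 to 9 at m = 2,000 and 7 to 11 at m = 250. For 12 to be the minimum at m = 2,000 in the unpaired comparison, the ICC would have to be about 0.039–0.043 (normal) or 0.036–0.039 (t), not 0.01.

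**Step 4: disease power on the survey, 12 per arm, ICC 0.01.**

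- Household as unit, m = 250: SE = √(0.043875 × 3.49 / 3,000) = 0.00714. Effect/SE = 2.0996. Power is 55.6% (normal), 51.9% (t), 54.1% (simulated).
- Person as unit, assuming 3–5 persons per household and ignoring household clustering, m = 750 to 1,250: DE = 8.49 to 13.49, effect/SE = 2.33 to 2.39. Power is 64.5–66.6% (normal) or 60.6–62.7% (t), so about 61–67%.

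**Step 5: dependence on the disease ICC.** The values 0.005 and 0.02 are assumptions, not in the documents. At m = 2,000 the normal power is 91.7% and 41.0%.

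**The case against.** Both powers printed for 12 clusters are correct, so the House Index complaint comes down to one word with no consequence for inference. That stands, and it is why the point is minor. It does not make the word right: no method tried gives 12 at the stated cluster size. The one variant that reaches 12 needs 200 households per cluster, doubled variance and a paired central t; the noncentral t then gives 11. Nor can 12 be explained as the number needed for disease. The text names no disease power target, and 80% at ICC 0.01 and 2,000 units would take 17 (normal) or 18 (t) clusters per arm.

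On disease, a reader might infer that the 68% is a miscalculation, or that its ICC and cluster size cannot be known. The documents support neither. The sentence follows the House Index inputs directly and presents itself as the same calculation. Carrying over 2,000 and 0.01 returns 67.8%, while 250 households return 55.6%. The ICC and cluster size are therefore implied and recoverable, and asking for the source and unit of the 3% is largely a request for missing detail. What remains is the mismatch of outcomes: the figure fits whole clusters, but DZC is not recorded for whole clusters.

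Quoting only the household figure would also be unfair, because the questionnaire records illness person by person. The person-level range belongs beside it.

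**Conclusion.** Wrong as written, and minor. The stated minimum of 12 per arm should be 3 or 5 at the plan's own inputs, and 4 or 6 with the houses actually surveyed (normal or noncentral t). A reader might infer that the House Index comparison is unsafe. It is not: 12 per arm gives about 100% power at either cluster size.

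The 68% is arithmetically sound for 2,000 units per cluster at an ICC borrowed from the House Index (64–68% from t to normal). It is not the power that the survey gives for DZC: about 52–56% by household, or about 61–67% by person under the assumed household sizes. For notified dengue, which the SAP does compare over whole clusters, the documents give no baseline rate, so the 3% cannot be taken to apply to it.

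These figures assume a two-sided test and an unpaired, post-intervention comparison. Pairing and difference-in-differences may raise or lower them.

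**What to change.** In both documents, delete the clause that calls 12 per arm the minimum needed, and state instead:

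> Twelve clusters per arm were chosen. They give more than 99% power for a 50% reduction in the House Index from 30% (ICC 0.01) with the 250 houses surveyed per cluster. For a fall in disease incidence from 3% to 1.5%, carrying over the House Index ICC of 0.01, power is about 64–68% (t to normal approximation) if whole clusters of 2,000 units are counted. If self-reported DZC from the survey is used, power is about 52–56% with the household as unit, or about 61–67% with the person as unit (assuming 3–5 persons per household and ignoring household clustering). These are unpaired, post-intervention figures.

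Say which source (survey or SIVIGILA) and which unit (household or person) the 3% refers to. If it is meant for notified dengue, give that baseline rate and recompute. Label any sensitivity to the ICC as an assumption.

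The cost is wording only, with no added clusters or data. The downside is that the stated disease power becomes less favourable.

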## Sampling procedure for household survey and entomological inspections

On the basis of available maps, the city was stratified into high, middle and low endemic/infested areas for *Ae. aegypti* (strata) using the surveillance information from SIVIGILA of the preceding year as well as information obtained from interviews with the vector control coordinators in Cúcuta. By this way, 24 high and medium endemic areas (clusters) were selected in Cucuta (16 clusters), Los patios (4 clusters) and Villa del Rosario (4 clusters). Figure 1 shows the selected clusters in

Cucuta to be sampled by staff. For the baseline study they were not yet paired and allocated to the intervention and control arm as this was planned to do with the information resulting from the baseline study enabling us to find pairs of clusters with similar characteristics. The following characteristic should be similar in each pair of clusters: (I) High and middle level endemicity for *Aedes*-borne diseases; (II) Similar socio-economic conditions; (III) Similar types of the built environment: houses, schools, industry, health centers, workshops, churches and stores; (IV) Similar characteristics of public spaces. Within each cluster, all blocks of houses were inspected including public spaces. For the entomological/socio-demographic household survey, a proportion of 10% of 2000 houses was sampled in this study, resulting in 200 houses in each cluster. This number was rounded to 250 by convenience. Therefore, the study targeted 6000 households (250 households in each cluster) using a systematic random sampling method. For this we first estimated the sampling interval by dividing the total number of households in each cluster (around 2000) by the number of sample households (250), resulting in a sampling interval of 8. All households located within each cluster were mapped and a randomly defined starting point was selected and from there every 8th household was visited. Clear replacement rules were given to the interviewers and the compliance was checked in sample of families.

Vector control staff and trained interviewers participated in the survey. They were divided into “couples” of one vector inspector and one interviewer. Each couple was assigned one cluster where they had to visit the sample houses. The interviewer did the interview with the head of household and simultaneously the inspector (local vector control staff) did the inspection of water containers both of them filling a form.

### Data collection

The baseline surveys included a household questionnaire and entomological survey (see Additional files). The instruments were discussed in a participatory workshop with experts and pre-tested among the members of vector control staff in the three municipalities leading to some modifications. The first instrument was the questionnaire which was applied by trained interviewers and the other part was the form for the entomological inspections (larvae/pupae survey) which was applied by the vector control staff. As this is part of the national vector control programme only verbal consent of the house owner was obtained to check their water containers. An extensive training was conducted by the research team before starting the field work.

## Household questionnaire

Demographic and health data was collected through face-to-face interviews using a standard questionnaire that included both structured and semi-structured questions. Household questionnaire was adapted from published research in Colombia [8]. The questions referred to socio-demographic parameters (number of people living in the house, age, sex, and educational level), self-reported DZC disease acquired during the last months, population mobility during the day, usage of water in tanks and willingness to accept the intervention trial (see Additional file).

## Entomological survey

The standard entomological survey form was adapted following the guidelines of Standard Operational Procedures (SOPs) by WHO [9]. The questions were adapted to local conditions and survey requirements (see Additional file). The following data were recorded from each household: total number of containers (potential breeding sites), number of mosquito larvae positive and negative containers (any species), pupae count per container, container type, and other container characteristics (if they were covered or uncovered, outdoors or indoors).

## Dengue surveillance and case definition

Data of the national surveillance system were obtained from SIVIGILA (the national health surveillance system), aggregated by year and setting (study areas) over the study period. Notified dengue cases including those classified as dengue fever (DF) and severe dengue, relying on a clinical case definition or lab confirmed or hospitalized patients. This study used annual population data (from the National Institute of Statistics-DANE; [10]) for calculating the incidence rate.

[figure not shown]
## Ethical considerations

The household questionnaire was only applied to adults who provided information related to the purpose of this study. No child or adolescent below the age of 18 was interviewed in this study. All people participating in the study were informed in local language through the study information sheet in a written and oral way. They were asked to sign the informed consent form. All participants were informed that their participation was voluntary and that their responses remained anonymous, therefore the study used numbers which replaced the names of individuals and codes which replaced the address of house. Before

examining the domestic and peri-domestic water-holding containers, the field team requested permission to enter the house, did the inspection and collected entomological and sociodemographic data.

The study received approval from local health authorities in Cucuta and Norte de Santander and the study protocol was approved by the ethical committee of the Albert-Ludwigs-Universität (application number 141/19) in Freiburg, Germany

## Fig. 1

Selection of clusters in Cucuta

Map shows the 16 clusters selected in Cucuta which were visited by interviewers and vector control staff

**Fig. 2**

A concrete ground tank for washing purpose

Concrete ground tanks for washing (*lavadero*) are made of cement or ceramic tiles with the shape of a rectangle or square and variable sizes

## Household questionnaire

### Form for extraction of socio-demographic data

*We are evaluating a new strategy against dengue. If you allow me, I will ask a few short questions that will not take up much of your time. If you feel uncomfortable with any question, you cannot answer or end the interview whenever you want.*

House code: \_\_\_\_\_

Cluster code: \_\_\_\_\_

**1. ¿ Could you give us the following details about the people who live in your house, including yourself in the following table?**

